## 8 SAFETY

---

### 8.1 SUBJECT DEATH

If a patient dies during or after deployment or retrieval of the Aortix Pump and the death is believed to be related to the device or procedure, the Investigator will make every effort to have an autopsy performed to help determine the extent to which the patient's death was related to the device/procedure. The Aortix pump should be returned to Procyron.

All subject deaths which occur in subjects prior to study exit/withdrawal, regardless of causality or study relationship, must be reported to Procyron. Investigator must provide a detailed narrative summary to include as much detail that is known regarding the circumstances surrounding the death. All deaths will be brought to the clinical event committee for adjudication and will be reported using standard mortality classifications.

## 8.2 ADVERSE EVENTS

Adverse event definitions used in the study are based on ISO 14155:2011 (Clinical Investigation of Medical Devices for Human Subjects – Good Clinical Practice) as defined below in Adverse Event Definitions:

**Adverse Event (AE):** Any untoward medical occurrence, unintended disease or injury, or untoward clinical signs (including abnormal laboratory findings) in participants, users, or other persons, whether or not related to the investigational medical device.

Note: This definition includes events related to the investigational medical device or the comparator. This definition includes events related to the procedures involved. For users or other persons, this definition is restricted to events related to investigational medical devices.

For purposes of this study, adverse events considered by the investigator to be related to the Aortix device system or Aortix device procedure or that are due to worsening kidney function postoperatively must be reported. Postoperative adverse events associated with the main surgical procedure such as nausea, bleeding, constipation or the like, when not related to the Aortix system, or diminished kidney function are not required to be reported. If adverse events related to the surgery but not to Aortix are reported, they should be indicated on the eCRF as being “not related” to study procedures.

**Adverse Device Effect (ADE):** Adverse event related to the use of an investigational medical device.

Note: This definition includes adverse events resulting from insufficient or inadequate instructions for use, deployment, implantation, installation, or operation, or any malfunction of the investigational medical device. This definition includes any event resulting from use error or from intentional misuse of the investigational medical device.

**Serious Adverse Event (SAE):** A Serious Adverse Event is an adverse event that:

- led to death
- led to serious deterioration in the health of the participant that resulted in:
  - a. a life-threatening illness or injury, or
  - b. a permanent impairment of a body structure or a body function, or
  - c. prolonged hospitalization, or
  - d. medical or surgical intervention to prevent life-threatening illness or injury or permanent impairment to a body structure of a body function

Note: Planned hospitalization for a pre-existing condition, or a procedure required by the Clinical Investigation Plan, without serious deterioration in health, is not considered a serious adverse event.

**Serious Adverse Device Effect (SADE):** An adverse device effect that has resulted in any of the consequences characteristic of a serious adverse event.

**Device Deficiency:** Inadequacy of a medical device with respect to its identity, quality, durability, reliability, safety, or performance.

Note: Device deficiencies include malfunctions, user errors, and inadequate labeling. They can be, but do not have to be, associated with an ADE or AE.

**Unanticipated Serious Adverse Device Effect (USADE) / Unanticipated Adverse Device Effect (UADE):** Serious adverse device effect which by its nature, incidence, severity, or outcome has not been identified in the current version of the risk analysis report (or protocol or instructions for use)

Note: Anticipated Serious Adverse Device Effect (ASADE) is an effect which by its nature, incidence, severity, or outcome has been identified in the risk analysis report. AEs or SAEs will also be classified as to their relationship to the Investigational Medical Device or procedure, as follows:

Relatedness should be classified by the Investigator. The following definitions shall be used to classify relatedness:

**Not Related:** The event is due to an underlying or concurrent illness or effect of another device, drug, or intervention and is not related to the investigational device or procedure. Not related can be used if the event is unlikely to be related.

**Related:** The event could be attributed to the use of the investigational device or the investigational procedure. Related classification can be used if the event is felt to be likely or probably related.

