#### 4.8.2.4 Every Twenty-Four Hours Post-Surgery ( $\pm$ 6 hours) until Day 7 Post-Surgery or Hospital Discharge (whichever comes first)

1. For patients with Aortix, continue to evaluate Aortix pump access site for bleeding or infection
2. Draw blood to monitor BNP and Serum Creatinine
3. Monitor and report any adverse events or deviations
4. Document medications used and medication changes
5. Record 24-hour urine output and fluid ins
6. Document use of any advanced renal supportive therapies such as dialysis or continuous renal replacement therapy (RRT)
7. Obtain post-operative notes daily, de-identify and provide to sponsor
8. Document any new diagnosis of postoperative Acute Kidney Injury
9. If patient remains hospitalized at day 7, document if prolonged admission is due to AKI (document as adverse event)

Prior to discharge, provide patient instructions for reporting any hospitalizations or device related adverse events. Provide an appointment for the study follow-up discharge visit.

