#### 4.8.2.5 Visit at Day 30 Post-Surgery ( $\pm$ 3 days)

1. Draw blood for monitoring of BNP and Serum Creatinine
2. Document and report any adverse events or deviations
3. If not discharged from index hospitalization by day 30 post-surgery, document if inability to discharge is due to AKI
4. Document and report any rehospitalizations including date and reason for hospitalization
5. Document use of any advanced renal supportive therapies such as dialysis or continuous renal replacement therapy (RRT)
6. Document days spent in ICU/CCU

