### 7.3 RISK MITIGATION

In addition, this protocol provides steps to mitigate risk to study patients. These include the following:

1. Limited Study Size: A limited number of patients will receive the Aortix Pump in this study to determine performance and safety.
2. Treatment Duration: The Aortix Pump is not a permanent implant and will only remain implanted during the scheduled surgery and at most for a limited time post-surgery.
3. Investigator Selection: The investigators in this study are selected based on their experience in performing large bore cardiovascular interventional procedures and experience treating patients with worsening renal function.
4. Site Selection: Study sites will have sufficient expertise and resources to manage the study.
5. Investigator Training: Investigator(s) will be trained in proper device operation prior to study start. Training will include didactic and hands-on training with the Aortix System.
6. Subject Screening: The study protocol includes appropriate precautions in patient selection. For example, patients with known anatomic incompatibilities or a significant bleeding risk are excluded.
7. Adverse Event Monitoring: Timely detection, treatment, and reporting of all adverse events.
8. Independent Safety Monitoring. Use of an external clinical events committee for safety monitoring with timely adjudication of adverse events.

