### 8.3 ADVERSE EVENT REPORTING REQUIREMENTS

Adverse events should be reported to Procyrion on the Adverse Event Electronic Case Report Form (AE eCRF) and using one eCRF per AE.

The Investigator must report SADEs and SAEs to Procyrion as soon as possible, but in no circumstances later than 24 working hours after the Investigator first learns of the event, at the following email address:

*By email to: [[contact]](mailto:[contact])*

The initial report must be followed by as much information is available and ideally should include complete documentation, including the time and date of onset, description of the event, severity, duration, actions taken and outcome (if known).

All AEs (regardless of severity or relationship to the study device) will be recorded on the eCRF.

Table 1: Timeline for Reporting of Adverse Events

Type	Report to	Reporting Timeframe (from time of learning of event)
Device Deficiency	Sponsor	Within 2 working days
AE / ADE	Sponsor	Within 2 working days
	EC/IRB	Per EC/IRB reporting requirements
SAE / SADE / USADE / UADE	Sponsor	Within 1 working day
	EC/IRB	Per EC/IRB reporting requirements

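### Section 8.2 makes surgical adverse events judged unrelated to Aortix or kidney function optional to report, with no exception for serious ones, while Section 8.3 requires every adverse event on the eCRF

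*Protocol*

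**What the plan says.** Section 8.2 gives the ISO-based definition of an adverse event (AE) and then sets a rule for this study. AEs that the investigator considers related to the Aortix system or its procedure, or due to worsening postoperative kidney function, must be reported. Other events of the main operation, such as nausea, "bleeding, constipation or the like, when not related to the Aortix system, or diminished kidney function are not required to be reported". The next sentence covers sites that enter such events anyway: "If adverse events related to the surgery but not to Aortix are reported, they should be indicated on the eCRF" as not related.

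Section 8.3 sets a different scope: "All AEs (regardless of severity or relationship to the study device) will be recorded on the eCRF". The same section names the form as the reporting route ("Adverse events should be reported to Procyrion on the Adverse Event Electronic Case Report Form (AE eCRF") and adds a rule for serious events: "The Investigator must report SADEs and SAEs to Procyrion as soon as possible". Table 1 then gives the sponsor deadlines: 2 working days for AEs and 1 working day for SAEs.

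Other sections use general wording. The daily in-hospital list (4.8.2.4) says "Monitor and report any adverse events or deviations", the day 30 visit (4.8.2.5) says "Document and report any adverse events or deviations", and the risk-mitigation list (7.3) promises "Timely detection, treatment, and reporting of all adverse events". Section 3.2.3 item 1 plans to report the rate of all AEs, deaths included.

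**The concern.** Which events a site must enter is a protocol instruction, and later analysis cannot recover events that were never collected. If some sites follow 8.2 and others 8.3, the numerator of the rate in 3.2.3 item 1 differs between sites for reasons unrelated to patients or device.

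The two arms are also affected differently. Section 3 says both arms share the same data collection apart from Aortix data, and that both will be reported. A patient without the pump can hardly have a pump-related event. Under 8.2 the compulsory set in that arm therefore shrinks essentially to kidney events, plus deaths under 8.1. A bleed attributed to Aortix would be counted in one arm, while surgical bleeds in the other could go unentered.

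The primary safety endpoint (3.2.1) counts SAEs related to Aortix. Bleeding is a named example in the 8.2 exemption and also a listed study risk in 7.2. Under 8.2 the investigator's own view of relatedness decides whether a bleed is entered at all, and the relatedness definitions allow an event to be classed as not related when a link is merely unlikely.

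**Working it through.** There is no stated figure to reproduce and no formula applies. The check sets the rules side by side for each kind of event.

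| Event | Section 8.2 (with 8.1 for deaths) | Section 8.3 |
|---|---|---|
| Non-serious surgical bleed, judged unrelated | Optional, no deadline | Mandatory, sponsor within 2 working days |
| Serious surgical bleed, judged unrelated | Optional, since no seriousness limit is stated | Mandatory, sponsor within 1 working day |
| AE related to Aortix or due to worsening kidney function | Mandatory | Mandatory |
| Death | Mandatory whatever the cause (8.1) | Mandatory |

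The sections disagree in the first two rows and agree in the last two.

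Two readings might reconcile the sections.

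1. *Recording differs from reporting.* On this reading 8.3 asks sites to record everything and 8.2 limits what they report. It fails because 8.3 makes the AE eCRF the means of reporting to the sponsor. Section 8.2 also treats eCRF entry of these events as conditional on a choice to report them.
2. *The specific rule overrides the general one.* On this reading 8.2 defines the study's scope and 8.3 only sets route and timing. It fails because 8.3 speaks of all AEs and expressly sets relationship aside, which is the attribute on which 8.2 exempts.

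The general phrases in 4.8.2.4, 4.8.2.5, 7.3 and 3.2.3 do not mention relatedness and settle nothing alone. They fit 8.3 and do not fit 8.2.

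**Patients covered:** 20 implanted (Section 3.4) + 30 as the cap on the non-treatment arm (Section 3.4) = up to 50.

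**Events lost:** not derivable, because the protocol states no frequency of surgical AEs.

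**The case against.** The strongest reply is that 8.2 permits and does not forbid. A site that enters every AE complies with both sections, so the exposure is under-reporting by sites that rely on 8.2. That is right, and it is how the conflict should be described: optional against mandatory.

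Second, 8.2 can be read as the scope rule for the study. Its compulsory set includes kidney events unrelated to the device, so the reference to relationship in 8.3 keeps some meaning inside that scope. This may be what the sponsor intended. The text of 8.3 still says all AEs, and on this reading 3.2.3 item 1 carries the wrong name, so one side has to change in any case.

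Third, that serious events are exempt is inferred from the absence of a limit in 8.2. Nausea and constipation are usually minor, and 8.3 has its own firm SAE rule. A careful site may well report serious events. The inference stands because bleeding can be serious and 8.2 makes no exception, but non-serious surgical AEs are the firmer part of the point.

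Fourth, there are safeguards. The clinical events committee may ask for unreported events to be added (10.5), and the sponsor receives operative notes, bypass records and daily postoperative notes (4.9). These help in hospital. The daily notes stop at day 7 or discharge, however, and a discharge summary is requested only when an AE has occurred, so later events may leave nothing to review.

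Finally, this is a small feasibility study in which patients are reviewed individually (Section 9), and the clear casualty is one descriptive outcome. That limits the consequence but does not remove the contradiction.

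**Conclusion.** The contradiction holds as the protocol is written. For surgical AEs judged unrelated to Aortix and to kidney function, 8.2 makes entry optional, 8.3 makes it mandatory, and nothing says which prevails. The direct effect is on 3.2.3 item 1: the rate would not be what its name says, its completeness could vary by site, and under 8.2 it would not be comparable between arms. For the primary safety endpoint this is only a risk. It runs through the investigator's relatedness judgement on serious surgical-type events and is partly covered by the SAE rule in 8.3 and by the committee. AEs related to Aortix, kidney AEs and deaths are compulsory on either reading.

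The conclusion rests on the wording alone. Its practical size depends on how many sites follow 8.2 and how often such events occur, and the protocol gives neither. It should be fixed before sites rely on the text.

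**What to change.** Reconcile the sections in one of two ways.

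1. **Collect everything.** Remove the exemption from 8.2 so that all AEs are entered in both arms through day 30. Sections 8.3, 4.8.2, 7.3 and 3.2.3 can then stay as they are.
2. **Keep a limited exemption.** Restrict it to non-serious surgical AEs. State in 8.2 itself that all SAEs in both arms are reported and go to the clinical events committee, whatever the investigator's view of relatedness. Align 8.3, 4.8.2.4, 4.8.2.5 and 7.3 with that scope, and rename 3.2.3 item 1 to the subset actually collected. Part of this repeats what 8.3 and 10.5 already say, but stating it beside the exemption removes the ambiguity.

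Either is a wording change with no new visits. The first option adds AE eCRF entries for at most 50 patients over 30 days; the second adds few. The cost is some extra data entry and committee review, and higher reported AE counts.

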## 3.2 STUDY ENDPOINTS

### 3.2.1 Primary Safety Endpoint

- 1) Rate of Occurrence of Serious Adverse Events related to the Aortix implant, retrieval, and therapy (rate will be calculated and reported) [timeframe: enrollment to 30 days post-surgery]

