### 7.2 POTENTIAL RISKS

The risks associated with trans-femoral interventions and mechanical circulatory support (MCS) are the predominant risks of the study. Most of the risks of the investigational Aortix System

procedure are similar to the risks associated with other percutaneous MCS devices, albeit the deployment location of the Aortix pump removes risk of mural thrombotic, or cerebral embolic events associated with MCS devices upstream from the carotid arteries. The likelihood of these risks is unknown since the use of MCS in this patient population has not been rigorously studied. These potential risks include, but are not limited to, the following:

- Access site pain or discomfort
- Allergic Reaction or Hypersensitivity
- Aortic Injury (including aortic puncture, tear, dissection or perforation)
- Anemia
- Bleeding (from the access site or due to anticoagulation therapy)
- Bruising at the Access Site
- Death
- Device Failure
- Device Malfunction
- Device Migration
- Embolism
- Hemolysis
- Hematoma
- Hepatic Injury
- Immune reaction
- Infection
- Insertion Site Hematoma
- Limb Ischemia
- Need for Additional Intervention (Surgical or Non-Surgical)
- Neurological Event
- Nerve Injury
- Pump Thrombosis
- Renal Injury
- Sepsis
- Syncope
- Thrombocytopenia
- Thromboembolic Complication
- Thrombotic Vascular Complication
- Vascular Injury (non-Aortic)
- Vascular Steal
- Wound Dehiscence

There may be other, unknown complications that may occur as a result of this procedure. If these or any of the above complications occur, they may lead to repeat or prolonged hospitalization, repeat procedures, emergency surgery, other emergency procedures, or, in rare cases, death. The study doctor and/or the research staff will make every effort to minimize additional risks.

The Sponsor has designed the device to be inherently safe. Failure modes due to the user, the device, or the software were studied and risks were mitigated through safe design, provision of information to the user, or protective measures in the medical device itself, software, or in the manufacturing process. The Aortix System is within acceptable risk levels as determined by the risk analysis conducted on potential hazard use, design, and software conditions.

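### The serious adverse event definition counts a prolonged stay but not a new admission, so some Aortix-related readmissions fall outside the primary safety rate

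*Protocol*

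**What the plan says.** The primary safety endpoint in Protocol section 3.2.1 is the "Rate of Occurrence of Serious Adverse Events related to the Aortix implant, retrieval, and therapy", from enrollment to 30 days after surgery.

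Section 8.2 defines what is serious. The event must have led to death, or to serious deterioration in health that in turn produced one of four results: (a) life-threatening illness or injury, (b) permanent impairment, (c) a longer hospital stay, or (d) an intervention to prevent a life threat or permanent impairment. Item (c) reads in full "c. prolonged hospitalization, or". The list has no open-ended item and no clause for medical judgement.

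The serious adverse device effect takes over the same list: "An adverse device effect that has resulted in any of the consequences characteristic of a serious adverse event". The unanticipated category is a subset of that one.

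Two other places bear on the intent:

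- The note under the list says that a planned admission for an existing condition, or a procedure that the plan itself requires, "without serious deterioration in health, is not considered a serious adverse event".
- Section 7.2 says of device complications that "they may lead to repeat or prolonged hospitalization, repeat procedures, emergency surgery" and other consequences.

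Readmissions are recorded in any case. The Day 30 visit (section 4.8.2.5) has the items "Document and report any adverse events or deviations" and "Document and report any rehospitalizations including date and reason for hospitalization".

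**The concern.** The safety window extends past discharge for every patient who leaves hospital before day 30. The protocol expects such discharges, because sections 3.2.2 and 3.2.3 both count readmissions. After discharge, the hospitalization event that can occur is a new admission, and that is the one the seriousness list does not name.

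Three things depend on the wording:

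- the seriousness class of the event;
- its reporting class, since Table 1 in section 8.3 gives the site 2 working days for an adverse event or device effect and 1 working day for a serious one;
- the count in the only primary safety endpoint.

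The effect on that count goes one way. Leaving out a class of related events can lower the rate but cannot raise it. Section 9 says the data will inform later trial design, so an understated rate would be carried forward.

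**Working it through.** The protocol states no figure to reproduce here. The check is a reading of the definition, followed by simple arithmetic for scale.

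**Step 1: apply the list as printed.** Take three Aortix-related events, each with serious deterioration:

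| Event | Criterion met | In the primary safety rate? |
|---|---|---|
| Keeps the patient in hospital longer, nothing more | (c) | Yes |
| Unplanned readmission, with an intervention to avert a life threat or permanent impairment | (d) | Yes |
| Unplanned readmission, with no death and none of (a), (b), (d) | None | No |

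The first and third rows can be the same complication. It counts if it arises before discharge and does not count if it arises after.

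**Step 2: compare the other passages.** Section 7.2 names repeat and prolonged hospitalization as two separate consequences, and section 8.2 carries over only the second. The note exempts planned admissions without serious deterioration. That exemption has little to do unless an unplanned admission with serious deterioration can make an event serious. Both passages suggest that new admissions were meant to count, but neither is a criterion.

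**Step 3: see whether another route captures the event.**

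- It stays reportable as an adverse event or device effect. The reporting scope in section 8.2 covers events related to the device or its procedure, and also those "due to worsening kidney function postoperatively must be reported".
- It appears among all-cause readmissions (section 3.2.3, item 5) and, if renal, in the third primary effectiveness endpoint (section 3.2.2).
- None of these feeds the rate in section 3.2.1.
- The clinical events committee reviews all events and its classification is final (section 10.5), but section 8.2 is the only list of seriousness criteria printed in the protocol.

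**Step 4: scale.** Section 9 gives up to 20 implanted patients. Section 3.2.1 does not fix the form of the rate. Assume it is patients with at least one event divided by implanted patients. Each affected patient with no other counted event then shifts it by 1/n:

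- n = 20: 1/20 = 5.0 points
- n = 15: 1/15 = 6.7 points
- n = 10: 1/10 = 10.0 points

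At n = 20 the exact (Clopper-Pearson) 95% intervals are:

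- 0/20 = 0%: 0 to 16.8%
- 1/20 = 5%: 0.1 to 24.9%
- 2/20 = 10%: 1.2 to 31.7%

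The protocol gives no discharge day. If it were day 7 or day 14 (assumed; both are marks used in section 3.2.3, item 6), the post-discharge part of the 30 days would be (30 − 7)/30 = 23/30 = 77% or (30 − 14)/30 = 16/30 = 53%. This is a share of time, not of events.

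**The case against.** The best reply is that the protocol's intent is clear enough. An investigator or the committee who reads (c) together with its note could class an unplanned readmission as serious, and section 8.2 says its definitions are based on ISO 14155:2011, which gives a reader something to fall back on. On this view the wording is incomplete rather than contradictory.

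The residual set is also small. The event must be Aortix-related, unplanned, after discharge and within 30 days. It must involve serious deterioration and yet escape (a), (b) and (d). The pump is out by the end of surgery, or after a suggested target of 48 hours (section 4.7), so exposure is normally over by discharge. Nothing is lost from the database, each patient's data are reviewed individually, and no threshold uses the rate (section 9).

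Much of this stands. The gap is narrow, criterion (d) will catch many device-related readmissions, and the count may be zero. The time shares above do not measure the size of the problem, since death and criteria (a), (b) and (d) apply on every day of the window. A shift of 1/n is also true of any single reclassified patient.

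The reply does not remove the point. Section 8.2 says the terms are used as defined there, so the printed list governs and the reference to the standard adds no criterion to it. If readers must infer a criterion from a note, two of them can class the same event differently, and the one who follows the text will leave it out.

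**Conclusion.** The concern holds. As written, the seriousness list leaves out an Aortix-related unplanned readmission with serious deterioration that meets no other criterion. The serious device effect categories inherit the omission, and such an event is left out of the primary safety rate to day 30.

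The number of affected events cannot be estimated from the protocol and may be zero. Per affected patient, the understatement is 5.0 points at 20 implants, 6.7 at 15 and 10.0 at 10. These figures assume a per-patient rate over implanted patients and no other counted event in that patient. The direction is certain: the rate can only be too low. The events are misclassified rather than lost, and no test or decision threshold depends on the rate. The point should be corrected, but it does not threaten the study.

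**What to change.** Reword criterion (c) in section 8.2 to *new unplanned in-patient hospitalization or prolongation of existing hospitalization*. Keep the requirement of serious deterioration above the list and the note on planned admissions below it, so that routine or elective admissions do not become serious events. The device effect definitions then follow without further change. State that the clinical events committee applies this wording to related rehospitalizations recorded at the Day 30 visit.

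The cost is a one-line amendment and matching wording on the electronic adverse event form. No new data are needed, because the date and reason of each rehospitalization are already collected. The price to the sponsor is a possibly slightly less favourable serious adverse event rate.

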## 10.5 CLINICAL EVENTS COMMITTEE (CEC)

An independent clinical events committee (safety committee) (CEC) will be utilized in this study for adverse event adjudication. All clinical events will be reviewed by the committee. The committee will consist of physicians who are not participating in the clinical study.

The sponsor will ensure that adequate source documentation is gathered prior to bringing an event before a committee. Additionally, the sponsor will remove all identifiers to site and patient. If an event goes to the CEC and the committee requests additional source documentation, the event will be listed as pending and every attempt will be made to bring the event back to the next meeting. Additionally, if upon review of the source documents, the CEC believes there is an adverse event that has not been reported, the CEC has the authority to request additional AE(s) be reported. Reports will show the CEC classification, once final as the final classification. In interim reports, pending events will be listed with the investigator classification. Deaths will be reported separately and the event leading to the death will be shown separately only if designated by the CEC as a separate event. Example, death from cardiac arrest is not reported as both a cardiac arrest and a cardiac arrest death.

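### The definition of Related sets two thresholds, so a possibly related serious adverse event can fall either side of the primary safety endpoint; adjudication covers this only in part

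*Protocol*

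**What the plan says.** The single primary safety endpoint in Protocol 3.2.1 is the "Rate of Occurrence of Serious Adverse Events related to the Aortix implant, retrieval, and therapy", from enrollment to 30 days after surgery.

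Section 8.2 defines relatedness in two classes, states that these definitions are mandatory, and names the first rater: "Relatedness should be classified by the Investigator".

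- *Related*, first sentence: "The event could be attributed to the use of the investigational device or the investigational procedure". Second sentence: "Related classification can be used if the event is felt to be likely or probably related".
- *Not Related*, first sentence, in part: "The event is due to an underlying or concurrent illness or effect of another device, drug, or intervention and is not related". Second sentence: "Not related can be used if the event is unlikely to be related".

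There is no intermediate class and no rule for choosing between the sentences.

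On reporting, Section 8.2 requires events that the investigator considers related to Aortix or due to worsening kidney function. Postoperative events associated with the main operation, "when not related to the Aortix system, or diminished kidney function are not required to be reported". Section 8.3 says that all adverse events go on the eCRF whatever their severity or relationship to the device, and that serious events go to the sponsor promptly.

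Section 10.5 sends all clinical events to an independent committee, which may ask for unreported events to be reported. "Reports will show the CEC classification, once final as the final classification"; until then, interim reports carry the investigator's classification for pending events.

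**The concern.** The endpoint is a count of events that pass a relatedness judgement, so the threshold for that judgement is part of the endpoint definition. If the threshold can be read two ways, two raters who both follow the protocol can return different counts from the same patients.

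Doubtful cases are foreseeable. The pump goes in through the femoral artery during the cardiac operation itself, under heparin (Section 4.5, Appendix C). Bleeding appears in Section 7.2 as a potential risk of the study and in Section 8.2 as an example of a surgical event that need not be reported when unrelated to Aortix. Embolism and limb ischemia are also listed risks. How often such events would be graded as merely possible cannot be known from the document.

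Section 9 says that the data will inform later trial design. A related-event rate whose threshold varies by rater is a weak basis for that. Adverse device effect and serious adverse device effect status rest on the same judgement.

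**Working it through.** The plan states no figure to reproduce. The check is textual, followed by a short illustration.

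**1. Four grades of causality against the four sentences of Section 8.2.** The grades are mine, used only to test the wording.

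| Grade | Related, sentence 1 (could be attributed) | Related, sentence 2 (likely or probable) | Not Related, sentence 1 (another cause) | Not Related, sentence 2 (unlikely) |
|---|---|---|---|---|
| Excluded | no | no | yes | yes |
| Unlikely | arguably yes | no | not necessarily | yes |
| Possible | yes | no | no | no |
| Probable or definite | yes | yes | no | no |

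A possible event is Related under the first sentence. A rater who takes the second sentence as the working threshold cannot call it Related and has only Not Related left, although the event is not unlikely. An unlikely event that could still be attributed to the device fits both classes. The wording can therefore err in either direction.

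**2. Whether the event reaches the committee.**

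- Section 8.2 makes reporting of a surgery-associated event depend on the investigator's own relatedness call. Section 8.3 records everything. The two conflict, and nothing says which governs.
- If a site follows Section 8.2, the committee can find an omitted event only in source documents. Section 4.9 supplies daily notes to day 7 or discharge, whichever is first, and a discharge summary only if an adverse event occurred. The endpoint runs to day 30. The day-30 visit (Section 4.8.2.5) does ask for adverse events, but is subject to the same conflict over which ones.
- Events due to worsening kidney function must be reported in any case (Section 8.2), and all deaths are reported and adjudicated (Section 8.1). Only their relatedness label is in doubt.
- The protocol gives the committee no relatedness threshold separate from Section 8.2.

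**3. Illustration of size.** Assumptions: all 20 planned implants take place and form the denominator, and the rate is the share of patients with at least one related serious event. Moving one patient changes the rate by 1/20 = 5 percentage points.

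Exact (Clopper-Pearson) 95% limits for x of n = 20 are the 0.025 quantile of Beta(x, n − x + 1) and the 0.975 quantile of Beta(x + 1, n − x); the lower limit is 0 when x = 0.

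| x/20 | Rate | 95% interval |
|---|---|---|
| 0 | 0% | 0 to 16.8% |
| 1 | 5% | 0.1 to 24.9% |
| 2 | 10% | 1.2 to 31.7% |
| 3 | 15% | 3.2 to 37.9% |
| 4 | 20% | 5.7 to 43.7% |

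The chance that at least one of 20 patients has a possibly related serious event is 1 − (1 − p)^20. For assumed p of 5%, 10% and 15% this is 64%, 88% and 96%. The document gives no value for p.

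**The case against.** The best defence is that the first sentence of Related is the definition and the second merely maps finer grades onto it. The second sentence is permissive and does not say that only likely or probable events qualify. A possible event meets neither sentence of Not Related, so the natural reading puts it under Related. This is a fair reading, and it means that loss of possible events is not inevitable. It does not make the text unambiguous: a sentence that names the grades suited to Related and omits possible invites the opposite reading.

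The second defence is adjudication. Section 10.5 covers all clinical events, makes the committee's classification final and lets it call for unreported events; Section 8.3 records every event. A reader might infer from the Section 8.2 exemption that adjudication fails altogether. The documents do not support that. They support a partial safeguard, limited by the missing committee threshold and the conflict between Sections 8.2 and 8.3.

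A reader might also infer that the endpoint is biased downward. That is not shown either, because unlikely events that could be attributed may be counted as Related. Renal injury is a poor example of an event that could go unreported, since kidney-function events must be reported regardless.

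Finally, the study is descriptive: Section 9 reviews patients individually, nothing is powered, and Section 3.2.1 sets no performance goal. Section 3.2.3 also reports all adverse events, so a reported event classed as unrelated stays visible. This limits the consequence but leaves the endpoint's definition unsettled.

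**Conclusion.** The conflict is real and should be corrected. Section 8.2 allows a possibly related serious event to be classed either way, and that call decides whether it enters the primary safety endpoint. For surgery-associated events it may also decide whether the event is reported. The supported conclusion is inconsistency between raters with a risk of undercounting, only partly covered by the committee.

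The size cannot be derived from the document. The 5 points per patient assumes 20 implanted patients and a patient-level rate; with fewer implants the step is larger (1/n). The counts and the values of p above are hypothetical. No power or type I error is affected, because none is claimed.

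**What to change.** 1. In Section 8.2, replace the second sentence of Related with: *Related is used whenever a causal contribution of the device or procedure is possible, probable or definite; Not related only when it is unlikely or excluded.* Align the second sentence of Not Related with it.
2. State in Section 10.5 that the committee uses the same threshold.
3. Reconcile the reporting exemption in Section 8.2 with Sections 8.3 and 10.5, so that every serious adverse event in an Aortix patient is reported and adjudicated whatever the investigator's relatedness call. The exemption can stay for non-serious surgical events if Section 8.3 is reworded to say so.

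The cost is a wording amendment, a few more events to document and adjudicate, and possibly a less favourable related-event rate. No change to sample size or visits is needed.
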